7.11. Concomitant Therapy or Medication

All concomitant medications will be coded using the WHO Drug. The concomitant medication will include all medications taken after the first study drug administration up to the end of the study.

The incidence of concomitant medications will be summarized using descriptive statistics by therapeutic class and PT. Patients are counted only once in each therapeutic class category, and only once in each PT category.

The subset of concomitant pain medication and medication or therapy for migraine/headache will be summarized by the following indication categories.

- opioids for reasons other than migraine/headache
- opioids for migraine/headache
- triptans and ergots
- NSAIDs for reasons other than migraine/headache
- NSAIDs for migraine/headache
- other

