3. STUDY DESIGN

3.1. General Design and Study Schema

This is an approximately 19-month, multicenter, randomized, double-blind, parallel-group study to evaluate the long-term safety, tolerability, and efficacy of sc TEV-48125 in adult patients with migraine. For patients who complete the pivotal efficacy studies of TEV-48125 (Studies TV48125-CNS-30049 and TV48125-CNS-30050), the study will consist of a 12-month treatment period and a 6.5-month follow-up period. For patients who have not participated in a pivotal efficacy study, the study will consist of a screening visit and 28-day run-in period, a 12-month treatment period, and a 6.5-month follow-up period.

Female and male patients 18 to 70 years of age, inclusive, with CM and EM who complete the pivotal efficacy studies (Studies TV48125-CNS-30049 and TV48125-CNS-30050) and approximately 300 patients (approximately half of whom have a diagnosis of CM and half of whom have a diagnosis of EM) who have not participated in the pivotal efficacy studies may enter this long-term safety, tolerability, and efficacy study if they meet the inclusion/exclusion criteria and provide informed consent. In addition, patients who do not complete the pivotal efficacy studies and those patients who complete the pivotal efficacy studies but do not wish to continue treatment during this long-term safety, tolerability, and efficacy study may attend a follow-up visit during this study for the purpose of ADA assessment approximately 7.5 months after their last dose of study drug.

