3.14. Study Procedures

Study procedures and assessments with their timing are summarized in [Table 1](#) (patients rolling over from the pivotal efficacy studies), [Table 2](#) (patients not rolling over from the pivotal efficacy studies), and [Table 3](#) (patients rolling over from the pivotal efficacy studies for ADA assessment only). Detailed by-visit information is provided in the sections following the table. Detailed descriptions of each assessment are provided in Section [6](#) (efficacy assessments), Section [7](#) (safety assessments), and Section [8](#) (pharmacokinetic and other assessments).

Table 1: Study Procedures and Assessments for Patients Rolling Over from the Pivotal Efficacy Studies

Study period	Pre-treatment period ^a	Treatment period													Follow-up period
		V1	V2 ^b	V3	V4	V5	V6	V7	V8	V9	V10	V11	V12	V13	
Procedures and assessments (completed before dosing, when applicable, unless otherwise noted)	Screening days -28 to -1	Dose 1 day 0 (±5 days)	Dose 2 day 28 (±5 days)	Dose 3 day 56 (±5 days)	Dose 4 day 84 (±5 days)	Dose 5 day 112 (±5 days)	Dose 6 day 140 (±5 days)	Dose 7 day 168 (±5 days)	Dose 8 day 196 (±5 days)	Dose 9 day 224 (±5 days)	Dose 10 day 252 (±5 days)	Dose 11 day 280 (±5 days)	Dose 12 day 308 (±5 days)	EOT/early withdrawal day 336 (±5 days)	Final visit day 533 (±15 days)
Informed consent		X													
Inclusion and exclusion criteria		X													
Randomization ^c		X													
Full physical examination, including weight		X ^d					X	X					X	X	X
12-lead ECG ^e		X ^d												X	
Vital signs measurement ^e		X ^d	X	X	X	X	X	X	X	X	X	X	X	X	
Clinical laboratory tests ^f		X ^d		X		X		X		X		X		X	
Urine β-HCG test ^g		X ^d	X	X	X	X	X	X	X	X	X	X	X	X	
Adverse events ^h		X ⁱ	X	X	X	X	X	X	X	X	X	X	X	X	X
Concomitant medication inquiry		X ^j	X	X	X	X	X	X	X	X	X	X	X	X	X ^k
eC-SSRS ^l		X ^d	X	X	X	X	X	X	X	X	X	X	X	X	X
Provide electronic headache diary device		X					X						X		
Complete electronic headache diary entries ^m		X	—————X				X	—X					X	—X	
Review electronic headache diary			X	X	X			X						X	
Return electronic headache diary device					X			X						X	

Clinical Study Protocol with Amendment 01

Study period	Pre-treatment period ^a	Treatment period													Follow-up period
		V1	V2 ^b	V3	V4	V5	V6	V7	V8	V9	V10	V11	V12	V13	

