3.14.3.1.11. End-of-Treatment Visit (Visit 14 [Day 336 ± 5 Days])

The following procedures/assessments will be performed at the EOT visit (visit 14):

- Review headache diary. (Note: Patients will return the electronic headache diary device at this visit.)
- Review study compliance.
- Perform vital signs measurements (includes systolic and diastolic blood pressure, pulse, body temperature, and respiratory rate).
- Perform 12-lead ECG.
- Perform physical examination (including weight).
- Inquire about adverse events.
- Inquire about/review concomitant medications.
- Complete the eC-SSRS Since Last Visit version.
- Perform clinical laboratory tests (serum chemistry, hematology, coagulation, and urinalysis).
- Perform urine β -HCG test (women of childbearing potential only).
- Administer the HIT-6 (patients with CM only), MIDAS questionnaire (patients with EM only), PGIC scale, MSQOL questionnaire, EQ-5D-5L questionnaire, WPAI questionnaire, and PHQ-2/PHQ-9. (Note: Patients will respond first to the PHQ-2. They will respond to questions 3 through 9 [unique questions] of the PHQ-9 only if the PHQ-2 is positive.)
- Obtain a 4-mL blood sample for plasma TEV-48125 concentration determination.
- Obtain a 5-mL blood sample for serum ADA assessment.
- Obtain a 5-mL urine sample for biomarker analysis.
- Obtain an 18.5-mL blood sample (6 mL each for serum and plasma and 6.5 mL for RNA) for serum, plasma, and RNA biomarker analysis.

In addition, a single 6-mL blood sample for pharmacogenomics (DNA) may be obtained from patients who consent to pharmacogenomics analysis if the sample is not obtained at an earlier visit.

After completing the EOT visit, patients may be treated with standard-of-care migraine treatment, as appropriate.

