9.7.2. Safety and Tolerability Analysis

All adverse events will be coded using the Medical Dictionary for Regulatory Activities. Each patient will be counted only once in each preferred term or system organ class category for the analyses of safety. Summaries will be presented for all adverse events (overall and by severity), adverse events determined by the investigator to be related to study treatment (ie, reasonable possibility; see [Section 7.1.4](#)) (defined as related or with missing relationship) (overall and by severity), serious adverse events, and adverse events causing withdrawal from the study. Patient listings of serious adverse events and adverse events leading to withdrawal will be presented.

Injection site erythema, induration, ecchymosis, and pain will be assessed, and severity will be graded as described in [Section 7.9](#), and findings will be listed and summarized.

Changes in laboratory and vital signs measurement data will be summarized descriptively. All values will be compared with prespecified boundaries to identify potentially clinically significant changes or values, and such values will be listed.

The use of concomitant medications will be summarized by therapeutic class using descriptive statistics. Concomitant medications will include all medications taken while the patient is treated with study drug.

Safety data will be summarized descriptively overall, by diagnosis, and by treatment group. For continuous variables, descriptive statistics (n, mean, SD, median, minimum, and maximum) will be provided for actual values and changes from baseline to each time point. For categorical variables, patient counts and percentages will be provided. Descriptive summaries of serious adverse events, patient withdrawals due to adverse events, and potentially clinically significant abnormal values (clinical laboratory or vital signs) based on predefined criteria will also be provided.

If any patient dies during the study, a listing of deaths will be provided and all relevant information will be discussed in the patient narrative included in the clinical study report.

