12.4. Declaration of the End of the Clinical Study

The end of the study is defined as the date the last patient attends the follow-up visit (visit 15) that will be performed approximately 7.5 months after the last dose of study drug. For clinical investigational centers located in the EU, a declaration of the end of the clinical study will be made according to the procedures outlined in Directive 2001/20/ED, Article 10(c); for other countries, local regulations will be followed.

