13. CHANGES TO PROTOCOL SPECIFIED ANALYSES

Not applicable.

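### SAP 7.11 counts medications up to the end of the study as concomitant, so its descriptive tables pool use during dosing with use after it, an undeclared departure from protocol 9.7.2

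*SAP*

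**What the plan says.** Protocol 9.7.2 gives the analysis definition, and the synopsis repeats it: "Concomitant medications will include all medications taken while the patient is treated with study drug". SAP 7.11 gives a different one: "The concomitant medication will include all medications taken after the first study drug administration up to the end of the study".

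SAP 7.11 does not define its end point. The protocol's only formal definition is in Section 12.4 (also in 3.1): "The end of the study is defined as the date the last patient attends the follow-up visit (visit 15"). Section 3.1 also says that, for rollover patients, "the study will consist of a 12-month treatment period and a 6.5-month follow-up period". New patients have the same two periods after their run-in.

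On what happens between EOT and visit 15, protocol 3.14.3.1.11 says: "After completing the EOT visit, patients may be treated with standard-of-care migraine treatment, as appropriate". Section 3.14.4.1 repeats the permission and schedules another medication inquiry at visit 15.

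SAP 7.11 then reports incidence by therapeutic class and preferred term, counting each patient once per category. It adds a subset table for triptans and ergots, opioids, NSAIDs and other. Neither table is divided by study period. The SAP Preface says that the SAP prevails over the protocol and that differences will be explained in the clinical study report (CSR). SAP 13, the section for changes to protocol-specified analyses, reads "Not applicable".

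**The concern.** The two definitions give different tables, and the one that governs adds a period of a different kind. During treatment, patients not on preventives are asked not to start any (protocol 3.1, Appendix B). After EOT, standard-of-care migraine treatment is permitted. With one pooled count, a reader of the CSR could not tell a preventive started during dosing from one permitted afterwards. The same holds for a first opioid, NSAID or triptan.

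Two further consequences follow. Patients who stop early and return about 225 days after their last dose contribute a larger share of post-dosing time, so the mix varies by patient. The interim CSR for the licence application (SAP 2.5.1) uses data up to a cut-off date, when some patients will not have finished follow-up. The same table could therefore rise between the interim and final reports only because the window lengthened.

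**Working it through.** **Inputs** (protocol Table 1; SAP Table 1 has the same days)
- Last dose: "Dose 12 day 308 (±5 days").
- End of treatment: "EOT/early withdrawal day 336 (±5 days").
- Final visit 15: day 533 (±15 days).
- Half-life: around 45 days (protocol 3.11).

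**The plan's own figure.** Follow-up = 533 − 336 = 197 days. This is 197/30.44 = 6.47 months, or 197/30 = 6.57 months, which matches the stated 6.5. From the last dose, 533 − 308 = 225 days = 5 × 45, which matches the stated five half-lives.

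**Share of the SAP window after EOT, completer.** 197/533 = 37%. With visit 15 at either end of its window: (518 − 336)/518 = 182/518 = 35% and (548 − 336)/548 = 212/548 = 39%.

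**Share for early withdrawal.** Assume that on-treatment time ends 28 days after the last dose and that the patient returns at 225 days. Then 225 − 28 = 197 days fall after treatment.

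| Last dose (day) | SAP window (days) | After treatment (days) | Share |
|---|---|---|---|
| 0 | 225 | 197 | 88% |
| 84 | 309 | 197 | 64% |
| 168 | 393 | 197 | 50% |
| 308 | 533 | 197 | 37% |

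**From calendar share to table rows.** These shares are not error rates. A patient who used a class before EOT is already counted and adds nothing in follow-up, so only first use after EOT changes a row. The documents give no usage rates, so the following rests on assumptions. Let r be the rate of first use per 28 days during treatment and k the multiplier on that rate after EOT.
- Incidence to EOT = 1 − exp(−r × 336/28).
- Incidence to visit 15 = 1 − exp(−r × 336/28 − k × r × 197/28).

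With r = 0.02, incidence to EOT is 1 − exp(−0.24) = 21%. To visit 15 it is 32% for k = 1, 41% for k = 2 and 55% for k = 4. Over r from 0.01 to 0.10 and k from 1 to 4, the ratio of the two incidences runs from 1.2 (r = 0.10, k = 1) to 2.9 (r = 0.01, k = 4). For a class that nearly everyone uses during treatment, the ceiling is low: if 90% are already counted, the ratio cannot exceed 100/90 = 1.11.

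**Residual drug.** By simple first-order decay, 2^(−28/45) = 65% of the amount present at the last monthly dose remains 28 days later, at EOT.

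**The case against.** The case for leaving the SAP as it is has real content.

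- **Follow-up is not drug-free.** With a half-life of around 45 days, washout is treated as complete only at visit 15. A reader might infer that the SAP mixes use on drug with use off drug. The documents support only a contrast between during dosing and after dosing. This stands, but the protocol's criterion is being treated, and follow-up is not treatment.
- **A long window suits a safety study.** Adverse events are collected through visit 15, so the medications given for them should be reported. This also stands. A separate follow-up table meets that need without pooling.
- **The protocol uses the word loosely.** Section 5.3 records concomitant therapy to the end of the study period. That is a collection rule; Section 9.7.2 defines the analysis.
- **The SAP's end point could be visit 14.** Protocol 3.14.4.1 treats patients who finish visit 14 in compliance with the protocol as having completed the study. Visit 15 is the more natural reading because it is the formal definition, but it remains an inference. If visit 14 was meant, the SAP still needs a sentence saying so.
- **There is a general remedy.** The Preface promises that differences will be explained in the CSR. An explanation would not separate the counts, and SAP 13 is where the change belonged.

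A reader might also take the EOT visit to be the protocol's cut-off. Section 9.7.2 names no visit. Patients who stop dosing early are encouraged to keep attending visits through EOT (3.14.4.1), so a plain EOT cut-off would itself count off-treatment use for them.

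**Conclusion.** The mismatch is real and minor. Followed as written, SAP 7.11 produces a different and less interpretable descriptive table than protocol 9.7.2, and SAP 13 does not say so. For a completer the window lengthens by about 197 days, assuming that the SAP's end point is visit 15.

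A reader might infer that 37% of reported concomitant use is misclassified, or that rebound use will be attributed to the drug. The documents support neither. The 37% is a share of time, the usage rates are not given, and no rebound is described. The ratios of 1.2 to 2.9 hold only for the assumed rates.

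Nor does the point reach the efficacy results. Days of acute medication use come from the e-diary for months 1, 2, 3, 6 and 12 (SAP 6.1 and 6.4.1.1). Discontinuation of preventives is bounded at EOT (SAP 6.4.1.2). No inferential analysis is planned (SAP 4.4), and concomitant medication is not a listed safety endpoint (SAP 7.1).

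**What to change.** In SAP 7.11, define on-treatment concomitant medication, in line with protocol 9.7.2, as any medication taken from the first dose in this study through the end of the treatment period:

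- completers: the EOT visit, consistent with the treatment period in SAP 4.6;
- patients who stop dosing early or are lost to follow-up: an analysis cut-off tied to the last dose, for example the last dose date + 27 days that SAP 7.2 already uses for patients lost to follow-up.

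Tabulate medications first taken after that point separately as follow-up medications, with the same classes and subset rows. Naming the first dose in this study matters because SAP 5.5 anchors rollover patients' prior medications to the pivotal study's first dose, while 7.11 does not say which first dose it means. If the longer window is intended, declare it in SAP 13, define the end of the study in 7.11, and split the table by period.

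The cost is a few sentences in the SAP, a date filter and one extra table. No new data are needed, since protocol 5.3 already requires start and stop dates.

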8. PHARMACOKINETIC ANALYSIS

There are no prespecified pharmacokinetic endpoints.

Summary of plasma concentration of the study drug will be based on the safety population and will be presented by visit for each of the indication and active treatment groups. The plasma concentration will be listed by indication, active treatments, scheduled visits, and time points.

9. BIOMARKER ANALYSIS

The biomarker analysis is not included in this SAP. A separate report will be provided.

10. PHARMACOKINETIC/PHARMACODYNAMIC ANALYSIS

The pharmacokinetic/pharmacodynamic relationship will be estimated and reported separately.

11. IMMUNOGENECITY ANALYSIS

The analysis of immunogenicity data is not included in this SAP. A separate report will be provided.

12. STATISTICAL SOFTWARE

All data listings, summaries, and statistical analyses will be generated using SAS®.

13. CHANGES TO PROTOCOL SPECIFIED ANALYSES

Not applicable.

APPENDIX A. E-DIARY QUESTIONNAIRE

The following questions are referring to yesterday (00:00 - 23:59)	
A1	Did you experience a headache of any severity yesterday
A2	Did you have at least four (4) consecutive hours of headache yesterday?
A3	Did you have at least two (2) consecutive hours of headache yesterday?
A4	What was the greatest severity that your headache reached yesterday at anytime?
A5	How many total hours did you have a headache(s) of any severity yesterday ?
A6	How many total hours did you have a headache(s) of moderate or severe intensity yesterday?

The following questions are referring to yesterday (00:00 - 23:59) AT THE TIME WHEN YOUR HEADCAHE REACHED THE WORST SEVERITY	
B1	Was it worse on one side of the head than on the other, and/or limited to one side of the head?
B2	Was it pounding, pulsating, or throbbing?
B3	Was it made worse by routine activities such as walking or climbing stairs?
B4	Did you have nausea, or get sick to your stomach?
B5	Did light bother you more than when you didn't have a headache (did you experience photophobia)?
B6	Did sounds bother you more than when you didn't have a headache (did you experience phonophobia)?
The following questions are referring to yesterday (00:00 - 23:59)	
B7	Did you experience something like seeing spots, stars, lines, flashing lights, zigzag lines, or "heat waves" around the time of your headache? (This is different from "light bothers you")
B8	Did you have feelings such as numbness or tingling in any part of your body or face around the time of your headache?
B9	Did you experience something like seeing spots, stars, lines, flashing lights, zigzag lines, or "heat waves" similar to those you may have seen when you have a headache? (This is different from "light bothers you")
B10	Did you have feelings such as numbness or tingling in any part of your body or face, similar to what you may have felt when you have a headache?

C0	Did you take any medications yesterday for your headache/migraine?
C1	Were any of the following Medications taken yesterday?
	Local list of Triptans, Ergots and Opioid combinations, Presented in groups of 5 per screen, with Yes / No option to answer.
	For the following questions please do not consider any medications you listed in the above questions.
D1	Did you use any other prescription medications (i.e opioids) in an effort to get relief from your headache/migraine?
D5	Did you use any other over the counter medications in an effort to get relief from your headache/migraine ?
E1	Did you have problems falling sleep last night?
E2	Which of the following situations best describe your work/school performance yesterday, when you did not have a headache?
E3	What would better describe in general, how did you feel yesterday?
E4	How much of the time yesterday did you find it difficult to concentrate on what you needed to do?
E5	On average, how much of the time yesterday were you very tired, asleep, or feeling drained?
E6	Which of the following situations best describe your ability to perform household chores yesterday, when you did not have a headache?
E7	How engaged were you with your partner's or children's activities yesterday, when you didn't have a headache?
E8	Overall, how interested were you in doing daily activities yesterday?

APPENDIX B. LOGICS FOR ENDPOINTS DERIVATION

headache day of at least moderate severity		
Primary endpoint CM		
OPTION 1		
1	A1	YES
2	A2	YES
3	A4	Moderate or Severe
OPTION 2		
1	A1	YES
2	C0	YES
3	C1	YES
4	C1	ERGOT OR TRIPTAN
OPTION 3		
1	A1	YES
2	C0	YES
3	D1	YES
4	D1	ERGOT OR TRIPTAN

CM migraine day: 1 of the following 5 options			
OPTION 1			
Part 1	1	A1	YES
	2	A2	YES
AND			
TWO OF THE FOLLOWING			
Part 2	1	A4	Mod-S
	2	B1	YES
	3	B2	YES
	4	B3	YES
AND			
ONE OF THE FOLLOWING			
Part 3	1	B4	YES
	2	B5	YES
			AND
	B6	YES	
OPTION 5: PROBABLE MIGRAINE			
If Part 1 and Part 2 met, Part 3 needs ONLY one of the following:			
Part 3		B5	YES
		B6	YES
If Part 1 and Part 3 met, Part 2 needs ONLY one of the following:			
Part 2	1	A4	Mod-S
	2	B1	YES
	3	B2	YES
	4	B3	YES

OPTION 2		
1	A1	YES
2	C0	YES
3	C1	YES
4	C1	ERGOT OR TRIPTAN
OPTION 3		
1	A1	YES
2	C0	YES
3	D1	YES
4	D1	ERGOT OR TRIPTAN
OPTION 4		
1	A1	YES
AND		
ONE OF THE FOLLOWING		
1	B7	YES
OR		
2	B8	YES

If **Part 2** and **Part 3** met, **Part 1** needs ONLY the following:

Part 1	1	A1	YES
---------------	---	----	-----

[figure not shown]
EM migraine day: 1 of the following 5 options			
OPTION 1			
Part 1	1	A1	YES
	2*	A2 or A3	YES
AND			
TWO OF THE FOLLOWING			
Part 2	1	A4	Mod-S
	2	B1	YES
	3	B2	YES
	4	B3	YES
AND			
ONE OF THE FOLLOWING			
Part 3	1	B4	YES
	2	B5	YES
AND			
		B6	YES
OPTION 2			
1	A1	YES	
2	C0	YES	
3	C1	YES	
4	C1	ERGOT OR TRIPTAN	
OPTION 3			
1	A1	YES	
2	C0	YES	
3	D1	YES	
4	D1	ERGOT OR TRIPTAN	
OPTION 4			
1	A1	YES	
	AND	ONE OF THE FOLLOWING	
1	B7	YES	
2	B8	YES	

[figure not shown]
* For eligibility evaluation, replace A2 or A3 = YES with A2='YES'.

OPTION 5: PROBABLE MIGRAINE			
If Part 1 and Part 2 met, Part 3 needs ONLY one of the following:			
Part 3		B5	YES
		B6	YES
If Part 1 and Part 3 met, Part 2 needs ONLY one of the following:			
Part 2	1	A4	Mod-S

[figure not shown]
	2	B1	YES
	3	B2	YES
	4	B3	YES
If Part 2 and Part 3 met, Part 1 needs ONLY the following:			
Part 1	1	A1	YES

APPENDIX C. HIT-6™ HEADACHE IMPACT TEST

[figure not shown]

[figure not shown]

[figure not shown]
APPENDIX D. THE MIGRAINE DISABILITY ASSESSMENT TEST

[figure not shown]

[figure not shown]
**APPENDIX E. MIGRAINE SPECIFIC QUALITY OF LIFE
QUESTIONNAIRE (MSQ) (VERSION 2.1)**

[figure not shown]

[figure not shown]

[figure not shown]

[figure not shown]
